PROJECT DESCRIPTION

Title: Attenuation of Stress Response Using Progesterone in Individuals with Alcohol Dependence and Post-Traumatic Stress Disorder NCT02187224

1. Principal Investigator:

[name]

Authorized Prescribers: [name] MD, [name] MD, [name] MD, [name] MD

2. Purpose:

Primary Aims:

1. To test if progesterone (PROG) is more effective than placebo in reducing craving after exposure to trauma or stress cues in a laboratory paradigm among men and women with a) comorbid AUD and PTSD and b) AUD only.

We hypothesize that progesterone in comparison to placebo will significantly reduce craving for alcohol in response to trauma cues in individuals with a) comorbid AUD and PTSD and b) AUD only. Craving for alcohol will be measured using a self-report Visual Analog Scale - Craving (VASC) and the Alcohol Urge Questionnaire (AUQ).

Secondary Aims:

1. To test if progesterone attenuates stress-induced anxiety, measured by the State Trait Anxiety Inventory (STAI-6).

2: To describe PROG's subjective mood effects, we will use the Differential Emotion Scale (DES-R)

3: To describe PROG's effects on cognitive performance, we will assess the ability to inhibit incongruent competing conflicts using the Stroop Color/Word test (Stroop).

Exploratory Aims:

1. To test if progesterone is more effective than placebo in reducing drinking and relapse during one month following exposure to trauma cues *using the Timeline Follow Back Method (TLFB)*.

2. To examine if there are gender differences in progesterone effects on stress and alcohol cue-induced craving.

We hypothesize that the effects of progesterone on stress and craving will be stronger in women than in men.

3. Background:

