Results: Dually diagnosed veterans reported significantly more craving for alcohol when exposed to trauma imagery than when exposed to stressful or neutral imagery ($p<0.001$) (Figure 1). The stress response decreased with treatment, and those with high stress response on prazosin reported greater, but not statistically significant, change in their drinking at the end of treatment (Figure 2). Also, there was a significant relationship ($r=0.603$) (Figure 3) between craving and the number of drinking days at follow up.

Conclusions: The preliminary findings show that veterans with dual diagnosis report strong craving after exposure to trauma

related imagery. **Based on this result we eliminated the stress condition for the present study.** The trauma-induced response predicted drinking at the end of treatment and at follow up.

- *These finding support the notion that reactivity to stress may increase the susceptibility for relapse.*
- *This study demonstrates that we have experience with this paradigm.*
- *It validates the ability of our research team to recruit individuals with AUD and PTSD.*

4. Significance:

To our knowledge, this study is the first to examine the ability of progesterone to reduce trauma or stress-induced craving in individuals diagnosed with a) comorbid AUD and PTSD and b) AUD only. Positive findings from this study will: 1) provide evidence that progesterone is important in mediating stress and alcohol craving, 2) provide insight into the underlying mechanisms of stress and alcohol craving, 3) help identify a potential marker that will distinguish who may be at

higher risk for alcohol relapse, and 4) provide a platform for other exploratory studies that can include the use of progesterone as treatment options for AUD and PTSD.

5. Research Plan:

Participants: Participants (N=72 completers) will be eligible for the study if they fullfill the following criteria:

Inclusion criteria:

- a) men (n=36) and women (n=36) age 21 to 60;
- b) have current diagnosis of *either*:
 - 1. AUD and comorbid PTSD
 - OR
 - 2. AUD

AUD will be determined by Structured Clinical Interview for DSM-5 (SCID-5) (First, Spitzer, Gibbon, & Williams, 2015). PTSD will be determined by Clinician Administered PTSD scale (CAPS-5)(Weathers et al., 2013) and by SCID-5);

- c) drink regularly (determined by TLFB and recorded 90 days prior to the interview);
- d) are not in an active phase of alcohol withdrawal;

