Initial Assessments: Participants will be interviewed with the SCID and CAPS for diagnostic evaluation. The TLFB(Sobell & Sobell, 1992) will be used to document the degree of daily alcohol consumption in the three months prior to study entry. Participants will have a psychiatric and medical examination by one of the investigators. Study data will be collected and managed using REDCap electronic data capture tools hosted at VA CT Healthcare System. REDCap

(Research Electronic Data Capture) is a secure, web-based application designed to support data capture for research studies, providing 1) an intuitive interface for validated data entry; 2) audit trails for tracking data manipulation and export procedures; 3) automated export procedures for seamless data downloads to common statistical packages; and 4) procedures for importing data from external sources (Harris et al 2009).

Screening and Baseline: Each participant will sign an informed consent. The study will be conducted with the approval of the VA Connecticut Human Subject Subcommittee. As part of the screening procedure detailed clinical assessment (to determine diagnosis), and medical assessments (physical exam, medical history, blood work and electrocardiogram) will be conducted. Those participants who fulfill all the inclusion and exclusion criteria will be enrolled in the study. On the first visit participants will be asked to come for a script development session. Also, women will be instructed to call the clinic when their menses starts and begin taking the study medication within the first 4 days of their menstrual cycle. The procedure is implemented in order to give some flexibility to female subjects and to ensure that they can finish the study during the early follicular phase (within the first seven days of the menstrual cycle).

Script Development Session: Scripts will be developed during a visit prior to the first laboratory session. Two scripts will be developed for each participant based on a procedure developed by our group. Participants with AUD and comorbid PTSD will develop one trauma related script and one neutral script. Participants with AUD only will develop one stress related script (since they have not experienced trauma) and one neutral script.

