Laboratory sessions: Laboratory sessions will be conducted on the Biological Studies Unit at the West Haven VA with trained personnel, and a psychologist or MD will be on call during the laboratory session. Additionally, all participants will be cleared by a study doctor prior to leaving the lab at the end of the imagery session (see Table 1 for details). Participants will be asked to arrive around 10:00 am. On arrival there will be a urine and breath alcohol concentration (BrAC) check. If clear to start an IV line will be placed. Those who test positive for any substance (other than marijuana) will be discharged. Blood pressure and pulse will be monitored continuously. Subjective measures of craving for alcohol, anxiety, affect, and cognitive functioning will be administered shortly after the set up. Prior to the presentation of the 1st and 2nd tapes, the relaxation technique will be used. Two conditions will be administered in a counterbalanced order: Trauma/Stress script and Neutral script. Subjective measures of craving, anxiety, affect, and cognitive functioning will be presented:1) prior to presentation of the scripts, b) immediately after presentation of each script, and c) following a 5 minute recovery period. After the last recovery period and assessments subjects will be encouraged to use the relaxation techniques. Craving and emotional distress will be evaluated throughout the session and subjects must return to baseline levels prior to being discharged from the unit. Subjects will wear an ambulatory physiological monitor (APM) (Eqvital EQ02, Vivonoetics, San Diego, CA) that collects continuous ECG, respiration, and activity for 20 minutes while at quiet rest at baseline, and throughout the stress challenge procedure. After completion of the scheduled portion of a session, any subject that reports residual craving or distress will participate in guided relaxation procedures with a clinically-trained psychologist for up to one additional hour. Relaxation has also been shown to reduce PTSD symptoms(Hamid & Neissi, 2009). If craving or emotional distress persists after an hour of relaxation training, the subject will receive an individual counseling session with a psychologist who is experienced in psychotherapy for PTSD. If craving or emotional distress persists after the psychotherapy session, the subject will be escorted to the Emergency Department and treated by the on-call psychiatrist.

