Method for data collection and analyses: Prior to performing statistical analyses, we will calculate descriptive statistics and will assess whether the distributions of all measures conform to normality. We will apply transformation or use nonparametric methods as necessary. We will estimate effect sizes in order to inform the design of potential future definitive studies. For the primary hypotheses we will use mixed effects models to assess change in stress reactivity after administration of progesterone vs. placebo. Study medication (progesterone and placebo), and gender will be a between subject factors, condition (trauma vs neutral) and time (pre, post and recovery following script presentation) will be used as within-subject factors. The primary stress reactivity variables will be craving. We will first compute descriptive statistics for each variable and will assess data distributions. All tests will be two-sided at 0.05 level of significance. We will use the Schwartz-Bayesian criterion (BIC) to select the best-fitting correlation structure within subject.

Study Duration: Two years.

6. References:

Allen, M. T., Boquet, A. J., Jr., & Shelley, K. S. (1991). Cluster analyses of cardiovascular responsivity to three laboratory stressors. *Psychosomatic Medicine*, 53(3), 272-288.

Blake, D. D., Weathers, F. W., Nagy, L. M., Kaloupek, D. G., Klauminzer, G., Charney, D. S., & Keane, T. M. (1990). A clinician rating scale for assessing current and lifetime PTSD: The CAPS-1. *Behavior Therapy*, 13, 187-188.

Bohn, M. J., Krahn, D. D., & Staehler, B. A. (1995). Development and initial validation of a measure of drinking urges in abstinent alcoholics. *Alcoholism, Clinical and Experimental Research*, 19(3), 600-606.

Brady, K. T., Killeen, T., Saladin, M. E., Dansky, B., & Becker, S. (1994). Comorbid Substance-Abuse and Posttraumatic-Stress-Disorder - Characteristics of Women in Treatment. *American Journal on Addictions*, 3(2), 160-164.

Breese, G. R., Chu, K., Dayas, C. V., Funk, D., Knapp, D. J., Koob, G. F., . . . Weiss, F. (2005). Stress enhancement of craving during sobriety: a risk for relapse. *Alcoholism, Clinical and Experimental Research*, 29(2), 185-195.

Bremner, J. D., Krystal, J. H., Southwick, S. M., & Charney, D. S. (1996). Noradrenergic mechanisms in stress and anxiety: II. Clinical studies. *Synapse*, 23(1), 39-51. doi: 10.1002/(SICI)1098-2396(199605)23:1<39::AID-SYN5>3.0.CO;2-1

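### The primary aim is posed separately for AUD with PTSD and for AUD only, but the primary model as listed has no diagnosis factor and no separate fits by diagnosis are stated

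*Combined protocol and SAP*

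**What the plan says.** **Aim.** Section 2 asks whether progesterone reduces craving after "trauma or stress cues in a laboratory paradigm among men and women with a) comorbid AUD and PTSD and b) AUD only". The hypothesis repeats the two populations: progesterone will "reduce craving for alcohol in response to trauma cues in individuals with a) comorbid AUD and PTSD and b) AUD only".

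**Model.** Under Method for data collection and analyses (section 5), mixed effects models are assigned to the primary hypotheses, with craving as the primary reactivity variable. The factors are: "Study medication (progesterone and placebo), and gender will be a between subject factors, condition (trauma vs neutral", followed by time (pre, post, recovery) as the other within-subject factor. Gender is in this list although it belongs to an exploratory aim: "To examine if there are gender differences in progesterone effects on stress and alcohol cue-induced craving".

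**Cues.** The two diagnostic groups do not hear the same active script. Those with PTSD develop a trauma script. For the others, Script Development Session says: "Participants with AUD only will develop one stress related script (since they have not experienced trauma) and one neutral script". Laboratory sessions uses the combined label: "Two conditions will be administered in a counterbalanced order: Trauma/Stress script and Neutral script".

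**Numbers.** Participants (section 5) sets 72 completers, split by gender only (36 and 36). Power Analysis recruits 36 to leave 30 with complete data in each *group*, without defining that word. Neither place gives numbers by diagnosis, and no stratification by diagnosis is described.

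**The concern.** The factor that defines the two parts of the primary aim is missing from the model meant to answer it. The listed factors can give a drug effect overall, or by gender, condition or time. Each of these is averaged over diagnosis.

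The average also runs over two stimuli. In the model text the active condition is called trauma, which does not describe what the AUD-only participants hear.

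The trial could therefore report on its primary aim without an estimate in either population that the aim names. The averaged figure would depend on the diagnosis mix enrolled, which the plan does not clearly fix. If the analyst split the data by diagnosis afterwards, that split would not be pre-specified.

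**Working it through.** **1. What the listed model can estimate.** Fully crossed, medication (2) x gender (2) x condition (2) x time (3) gives 24 fixed-effect parameters. None is indexed by diagnosis. Adding diagnosis crossed with medication, condition and time, without gender-by-diagnosis terms, adds 2 x 2 x 3 = 12, for 36. Only then does the model contain a drug contrast for 1a and another for 1b.

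**2. What averaging does (assumed effects).** If the share w of participants with AUD and PTSD is the same in both arms, the averaged contrast is w x (effect in AUD with PTSD) + (1 - w) x (effect in AUD only).

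- w = 1/2: (0.8, 0), (0.6, 0.2) and (0.4, 0.4) SD all give 0.40.
- w = 1/3: (0.8, 0) gives 0.8/3 = 0.27.
- w = 2/3: (0.8, 0) gives 1.6/3 = 0.53.

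These values show that the averaged result cannot separate such cases. They are not estimates of anything in this trial.

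**3. The plan's own power figure.** Power Analysis states 80% power with n = 30 at d' = 0.50, two-sided 0.05, as a within-subject comparison. The normal approximation gives n = ((1.960 + 0.842)/0.50)² = 31.4, and 78.2% power at n = 30. The exact paired t gives 75.4%. The 36 recruited is 30 x 1.2. The figure is thus roughly reproduced, but it contains no diagnosis term and says nothing about 1a or 1b separately.

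**4. Precision once each diagnosis has its own contrast.** Assumptions: 1:1 arms (no ratio is stated), an even diagnosis split, and 60 or 72 completers, so 60/4 = 15 or 72/4 = 18 per arm per diagnosis. d is in SD units of the chosen contrast, a between-arm reading of the plan's 0.50. Power is from the two-sample noncentral t; the standard error is sqrt(2/n).

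| Per arm per diagnosis | 95% CI half-width | Power at d = 0.50 | d for 80% power |
|---|---|---|---|
| 15 | 2.048 x 0.365 = 0.75 | 26% | 1.06 |
| 18 | 2.032 x 0.333 = 0.68 | 31% | 0.96 |

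With 72 completers and an AUD-with-PTSD share between 25% and 75% (9 to 27 per arm), power in that stratum runs from 17% to 44%.

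**5. The choice of contrast matters.** Suppose a residual SD of 0.5 per measurement. Pre-to-post change in the active script then has SD 0.5 x sqrt(2) = 0.71; that change minus the neutral-script change has SD 0.5 x sqrt(4) = 1. A raw effect of 0.5 is 0.71 SD on the first scale and 0.50 SD on the second. Power per diagnosis is 46-54% against 26-31%, provided the drug does not affect the neutral change.

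**6. Error control.** Two independent contrasts at 0.05 carry 1 - 0.95² = 9.75% familywise error. At 0.025 each, power at d = 0.50 is 18-21%. If both must succeed at 0.05, no adjustment is needed, but joint power is about 0.262² = 7% to 0.308² = 9%, with d = 0.50 true in both groups and independent estimates.

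**The case against.** The strongest reply is that the analysis text is one short paragraph and separate fits were meant. It speaks of hypotheses and models in the plural, and the trauma label would fit a model run in the PTSD group alone. This stands as a possibility. But two craving measures would explain the plurals equally well: "Craving for alcohol will be measured using a self-report Visual Analog Scale - Craving (VASC) and the Alcohol Urge Questionnaire (AUQ". The trauma label could also be text carried over from another design. A reader might infer two diagnostic groups of 36 from the total of 72. The documents do not support that: the 36 in Power Analysis is a number recruited, the 72 are completers, and the only explicit 36/36 split is by gender.

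A second reply is that the paragraph names no interactions either, so its silence on diagnosis is not a decision to pool. That is fair as to intent. It does not change what the listed factors can deliver.

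A third is that the strata are too small. They are, but this limits precision; it does not remove two estimates that the aim asks for. The same paragraph says that effect sizes will inform later studies, which estimates by diagnosis would serve.

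A reader might also infer from the pilot that averaging hides a real difference by diagnosis. The pilot result is: "Dually diagnosed veterans reported significantly more craving for alcohol when exposed to trauma imagery than when exposed to stressful or neutral imagery". That compares cues within dually diagnosed veterans. It does not compare trauma in one diagnosis with stress in the other, and it says nothing about progesterone.

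**Conclusion.** The point holds as a mismatch between aim and model. As listed, the primary model gives only drug contrasts averaged over diagnosis and over two active cues, and it does not estimate 1a or 1b. It would go too far to say that the sponsor chose to pool, or that 1a and 1b will certainly go unestimated; the plan simply does not state how they are obtained.

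The size of any distortion cannot be derived from the documents. No passage shows that the drug effect differs by diagnosis. Low power after the repair reflects the sample size and the contrast chosen, not the added term; the power figures rest on the assumed 1:1 allocation and even split.

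**What to change.** - Add diagnostic group and its interactions with medication, condition and time to the primary model, or state separate fits by diagnosis. Report the progesterone-placebo craving contrast with a 95% CI within each diagnosis as the estimates for 1a and 1b.
- Relabel the condition as trauma/stress versus neutral, and state that any difference between diagnoses is confounded with cue type.
- State in advance which contrast is used: active-script pre-to-post change, or that change minus the neutral change.
- State whether the two estimates are tested under a multiplicity rule, jointly required, or reported as estimation only. This and the contrast are the sponsor's choices; the documents do not dictate either.
- Define *group* in Power Analysis.

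The cost is wording in the analysis section. Diagnosis is already established by SCID-5 and CAPS-5, so no new data or visits are needed. The text should disclose the limited precision within each diagnosis: under the assumptions above, 80% power needs d of about 1.06 to 0.96.
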